5.1.1. Description of Study Days

Definition of Gap between Parent Study and 9HB01EXT

A gap is calculated as:

Date of Visit 1 for study 9HB01EXT – date of the last day of the parent study,

where the last day of the parent study is defined as either 1) the date of the last rFIXFc dose for subjects on a prophylactic regimen in study 998HB102 or 9HB02PED, or 2) the date of the last non-safety follow-up study visit for subjects on the episodic regimen in study 998HB102 or subjects in the surgery subgroup who ended the study in a surgical/rehabilitation period in study 998HB102 or 9HB02PED.

A listing will be provided for subjects from study 998HB102 who had a gap of greater than 14 days and subjects from study 9HB02PED who had a gap of greater than 7 days. These gaps were identified because for the majority of the subjects, the FIX activity would be anticipated to be below 1% after 14 days for subjects from study 998HB102 and to be below 1% after 7 days for subjects from study 9HB02PED. In addition, the definition of Study Day 1 will be somewhat different for these subjects with a longer gap, as described below.

For simplicity, the gap of greater than 14 days for subjects from study 998HB102 and the gap of greater than 7 days for subjects from study 9HB02PED will be referred to as the gap of greater than 14 or 7 days.

Definition of 9HB01EXT Study Day 1

9HB01EXT Study Day 1 will be used as a reference date to calculate the study day relative to the start of study 9HB01EXT. The definition of 9HB01EXT Study Day 1 depends on the length of the gap.

For 9HB01EXT subjects with no gap or a gap of less than or equal to 14 or 7 days:

9HB01EXT Study Day 1 is defined as the last day of the parent study, i.e. either 1) the day of the last rFIXFc dose for subjects on a prophylactic regimen in study 998HB102 or 9HB02PED, or 2) the day of the last non-safety follow-up study visit for subjects on the episodic regimen in study 998HB102 or subjects in the surgery subgroup who ended the study in a surgical/rehabilitation period in study 998HB102 or 9HB02PED.

For 9HB01EXT subjects with a gap of greater than 14 or 7 days:

9HB01EXT Study Day 1 is defined as either 1) the date of the first rFIXFc dose in study 9HB01EXT for subjects on a prophylactic regimen at the start of study 9HB01EXT, or 2) the day of the first study visit for subjects starting study 9HB01EXT on the episodic regimen or in a surgical/rehabilitation period.

Definition of Study Day

The following definition of Study Day will be used in the analysis:

- 9HB01EXT Study Day: day relative to 9HB01EXT Study Day 1, as defined above.

The start/stop day of events will be calculated as (date of event – date of Study Day 1 + 1) if the date of the event is on or after the Study Day 1 date, or (date of event – date of Study Day 1) if the date of the event is before the Study Day 1 date. Study Day -1 is the day immediately preceding Study Day 1. There is no Study Day 0 in this study.

5.1.2 Definition of Study 9HB01EXT Baseline

Study 9HB01EXT Baseline is defined as the last non-missing measurement taken at the scheduled 9HB01EXT study Visit 1 (See Protocol Section 4.1 for the definition of Visit 1). Eligible subjects will be enrolled at End of Treatment (EOT) visit of their parent study (998HB102 or 9HB02PED), which will serve as the Baseline Visit for this extension study. Baseline visit assessments may have been repeated if there was a gap in study treatment (e.g. a gap of greater than 37 days following the EOT Visit for the previous study).

If the baseline occurred coincidentally within a major surgical/rehabilitation period, it would be set as missing in the summary tables except for inhibitor and anti-rFIXFc antibody analysis.

5.1.3 Data Analysis

Unit body weight dose (IU/kg) for analysis of dosing will be calculated as the total IU (nominal dose) for each injection divided by the subject's most recent weight in kilograms prior to the dose of study drug.

Summaries on change from baseline by study visit will be based on subjects who have both study 9HB01EXT baseline and post-baseline values at the visit being summarized. Each of the post-baseline timepoint summaries will contain a row that provides the mean baseline value for the subjects included in that visit summary.

Post-baseline values are defined as any assessment taken after 9HB01EXT Study Visit 1. In the case of a post-baseline value at the scheduled visit is missing, the first non-missing assessment for that corresponding unscheduled visit will be used for by-visit summaries.

5.1.4 Handling of Missing Data

Aside from the following, no imputation of study data will be performed.

- The episodic treatment regimen at the start of study 9HB01EXT will be imputed for the scenario specified in Section 5.3.1.
- The occurrence of a new bleeding episode will be imputed if >72 hours lapse between 2 consecutive injections administered to treat a bleed. Details are provided in Section 7.1.1.

For CHO-KLAT, if a subject has data missing at a particular visit, the total score can still be estimated provided at least 27 of the 35 questions have been answered. If a subject's data cannot be used to calculate an overall score that subject will also be excluded from summaries of individual domains at that visit and will be flagged as excluded from summaries in analysis dataset. Details are provided in Section 7.5.3 and Appendix E.

For HAEMO-QoL and HAEM-A-QoL, and Hemo-Sat, if a subject has data missing at a particular visit for a domain, the total score and subscores will still be estimated provided the questionnaire makes provision for missing domains in the calculation algorithm of overall score. If a subject's data cannot be used to calculate an overall score that subject will also be excluded from summaries of individual domains at that visit and will be flagged as excluded from summaries in the analysis dataset. Details are provided in Sections 7.5.1 and 7.5.2 Appendix C, and F, respectively.

For the analysis of AEs and concomitant medications/procedures, if the stop/start date of an AE/concomitant medication is missing or partial, the corresponding study day will be left blank. However, inferences will be made from the partial and missing dates to classify medications as concomitant, AEs as treatment emergent (or not), and AEs during surgical/rehabilitation period. These inferences are described in Sections 6.4.1 and 8.2, respectively.

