Example: A raw score of 20 on the “Physical Health” Scale is to be transformed:

- when all 7 questions were answered:
 - minimal possible score = 7
 - maximal possible score = 35
 - range of scores = 28
 - TSS = $20 - 7 / 28 = 46.4$
- when 6 of the 7 questions were answered:
 - minimal possible score = 6
 - maximal possible score = 30
 - range of scores = 24
 - TSS = $20 - 6 / 24 = 58.3$

Transformed scores can be produced from raw subscale and raw total scores.

The total transformed score will be presented in outputs.

6. Presentation of scores

The transformed scores for subscale and total will be presented in the outputs.

7. Subscales

The following sub score categories are included for the HAEMO-QoL (Children and Teenagers aged 13-16) questionnaire:

Time Period	Sub-scores for HAEMO-QoL	No. of questions	No. of non-missing items required to calculate subscale
During the past month	1. Physical health	7	6
	2. Feeling	8	6
	3. View of yourself	10	8
	4. Family	8	6
	5. Friends	4	3
	6. Perceived Support	4	3
	7. Other person	6	5
	8. Sports and School	9	7
	9. Dealing with Hemophilia	7	6
	10. Treatment	8	6
	11. Future	4	3
	12. Relationships	2	2
	Total Score	77	63

The following sub score categories are included for the HAEMO-A-QoL (Adults) questionnaire:

Time Period	Sub-scores for HAEM-A-QoL	No. of questions	No. of non-missing items required to calculate subscale
During the past month	1. Physical Health	5	4
	2. Feeling	4	3
	3. View of yourself	5	4
	4. Sports and leisure	5	4
	5. Work and school	4	3
	6. Dealing with hemophilia	3	3
	7. Treatment	8	6
Recently	8. Future	5	4
	9. Family planning	4	3
	10. Partnership and sexuality	3	3
	Total Score	46	38

8. Sub score Items

Provided below is a copy of both questionnaires. Items are highlighted when they require re-coding as detailed in point 2 above.

HAEMO QoL Child and Teen Questionnaire

[III,kids,long] – CIII-HAEMO-QOL-USA/English –Final Version-29 Jun 07

HAEMO - QOL

Questionnaire for Children and Teenagers	Kids' long Version	age: 13-16
--	--------------------	------------

Hello there!

We would like to find out how you have been feeling during the past weeks, so we have worked out a few questions that we would like you to answer.

This questionnaire was designed for teenagers with hemophilia.

- ⇒ Please read each question carefully.
- ⇒ Think about how things have been for you over the past weeks.
- ⇒ Choose the answer that fits you best and put an "X" in the appropriate box.

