Questionnaire for Adults

Dear Patient,

We would like to find out how you have been feeling during the past weeks. Please be so kind as to answer the following questions in this questionnaire, designed specifically for people with hemophilia.

Please follow the instructions below when answering the questions:

- ⇒ Please read each question carefully.
- ⇒ Think about how things have been for you over the past weeks.
- ⇒ Put an "X" in the box corresponding to the answer that fits you best.
- ⇒ Only mark one box for each question.
- ⇒ There are no right or wrong answers.
- ⇒ It's what you think that matters.
- ⇒ There are some aspects that might not concern you (Sports & Leisure, Family Planning, Work & School, e.g., if you don't work or don't go to school). In such a case, please mark the answer category "not applicable."

All your answers will be treated with the strictest confidence!

Date of completion: ___ / ___ / ___ (month/ day/ year)

**1. Here we would like to find out about hemophilia and your
PHYSICAL HEALTH**

In the past month...	never	rarely	sometimes	often	all the time
1. ... my swellings hurt					
2. ... I had pain in my joints					
3. ... it was painful for me to move					
4. ... I had difficulty walking as far as I wanted to					
5. ... I needed more time to get ready because of my condition					

2. and now about how you have been FEELING because of your hemophilia

In the past month...	never	rarely	sometimes	often	all the time
1. ... my hemophilia was a burden for me					
2. ... my hemophilia made me angry					

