APPENDIX F. HEMO-SAT SCORING ALGORITHM AND QUESTIONNAIRE

The Hemo-Sat Patient Satisfaction scale is a 35-item questionnaire encompassing 6 subscales regarding the subject’s and parent/caregiver’s satisfaction with various aspects of the treatment and care the subject.

1. Scoring

The items presented in the Hemo-Sat questionnaire are worded in both positive and negative directions whereas the responses to the questions are consistently scored as 1=Totally agree, 2=Somewhat agree, 3=Neither agree nor disagree, 4=Somewhat disagree, and 5=Totally disagree. Therefore, the negatively-worded questions need to be rescored as 5=Totally agree, 4=Somewhat agree, 3=Neither agree nor disagree, 2=Somewhat disagree, and 1=Totally disagree so that a high score represent a high satisfaction with the treatment. After the rescoring the unidirectional values can be added to yield 6 subscores and a total score.

Negatively worded questions include numbers 9 through 11. The 32 remaining questions are all positively worded.

2. Producing the raw total and subscale scores

The raw total score is produced by summing up all of items that were answered across all 35 questions. Its range lies between the number of items answered \times 1 and the number of items answered \times 5. The highest possible score is 175. Applying a minimum data rule of 75%, at least 27 questions must be answered in order to obtain a total score.

Similarly, a raw subscale score is produced by summing up all items that were answered within a subscale. The range of values lies between the number of items that were answered \times 1 and the number of items that were answered \times 5 in a given subscale. The minimum number of questions answered for each subscale, applying a minimum data rule of 75%, is as follows:

Hemo-Sat Subscale	Number of questions	Number of non-missing items required to calculate subscale
1. Ease and convenience	11	9
2. Efficacy	6	5
3. Burden	4	3
4. Specialist/Nurses	7	6
5. Center/Hospital	5	4
6. General satisfaction with the treatment	2	2
Total score	35	27

3. Transferring a raw score to a Standardized (average) score

The Standardized score is the average of all items with a nonmissing score. That is, missing items do not contribute to either the numerator or denominator. This effectively imputes the

mean of all nonmissing items for the items that are missing, allowing for a comparison between subscales.

4. Transferring a raw score to a Transformed Score between 0 and 100

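### SAP 5.1.4 removes scorable HAEM-A-QoL and HAEMO-QoL domains whenever the total score cannot be calculated, overriding the domain minima in Appendix C

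*SAP*

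**What the plan says.** SAP 5.1.4 covers HAEMO-QoL, HAEM-A-QoL and Hemo-Sat together. When data are missing, total and subscores are still estimated "provided the questionnaire makes provision for missing domains in the calculation algorithm of overall score". If no overall score can be produced, "that subject will also be excluded from summaries of individual domains at that visit", and he is flagged in the analysis dataset.

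SAP Appendix C tabulates, for each domain and for the total, the number of questions and the "No. of non-missing items required to calculate subscale". Responses are coded 1 to 5. The transformed score takes its minimum and maximum from the number of questions answered, so a domain score draws on nothing outside that domain.

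The HAEM-A-QoL form printed in Appendix C tells the respondent: "There are some aspects that might not concern you (Sports & Leisure, Family Planning, Work & School", and directs him to the not-applicable option where that is so. Every item in those three domains has the box.

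SAP 7.5.1 plans by-visit summaries of the total and of each sub-score, with change from baseline, on the FAS.

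**The concern.** Appendix C sets a data-sufficiency rule for each domain. SAP 5.1.4 then adds a second condition, a calculable total, that the domain scoring does not need. Where the two conflict, valid domain scores are discarded because of gaps elsewhere in the form.

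The matter is sharper for HAEM-A-QoL because some gaps arise by design. A respondent who skips nothing and follows the instructions may leave items without a score. Whether sport, work or study, and family planning apply to a man is plausibly linked to his age and disability, so any loss may not be random. It would also reach domains such as Physical Health and Treatment that he answered in full, and the set of contributing subjects could change from visit to visit.

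**Working it through.** **Inputs** (all from the Appendix C tables, items / minimum):
- HAEM-A-QoL: Physical Health 5/4, Feeling 4/3, View of yourself 5/4, Sports and leisure 5/4, Work and school 4/3, Dealing with hemophilia 3/3, Treatment 8/6, Future 5/4, Family planning 4/3, Partnership and sexuality 3/3. The total row reads "Total Score 46 38".
- HAEMO-QoL: 7/6, 8/6, 10/8, 8/6, 4/3, 4/3, 6/5, 9/7, 7/6, 8/6, 4/3, 2/2. The total is 77/63.

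**Step 1. Reproduce the table.** The items sum to 5+4+5+5+4+3+8+5+4+3 = 46 and to 7+8+10+8+4+4+6+9+7+8+4+2 = 77, as printed. Every domain minimum equals 75% of its items, rounded up. The total minima do not follow that pattern: 38/46 = 82.6% and 63/77 = 81.8%, whereas 75% rounded up gives 35 and 58. No derivation of 38 or 63 is given.

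**Step 2. Sum the domain minima.**
- HAEM-A-QoL: 4+3+4+4+3+3+6+4+3+3 = 37, one short of 38.
- HAEMO-QoL: 6+6+8+6+3+3+5+7+6+6+3+2 = 61, two short of 63.

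A subject exactly at every minimum has all 10 (or all 12) domain scores but no total, and 5.1.4 drops all of them. This step does not depend on how not-applicable answers are read.

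**Step 3. Not-applicable answers (HAEM-A-QoL only).** The three domains are "4. Sports and leisure 5 4", "5. Work and school 4 3" and Family planning with 4 items, so 5+4+4 = 13 boxes. Assume that not applicable is unscored and that nothing else is blank:

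| Domains marked not applicable | Items left | Total (needs 38) | Other domains, fully answered |
|---|---|---|---|
| Sports | 46−5 = 41 | yes | 9 |
| Work, or Family | 46−4 = 42 | yes | 9 |
| Work + Family | 46−8 = 38 | yes, no margin | 8 |
| Sports + Work, or Sports + Family | 46−9 = 37 | no | 8, all dropped |
| All three | 46−13 = 33 | no | 7, all dropped |

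The total tolerates 46−38 = 8 unscored items, so at least 9 of the 13 boxes are needed. After Work + Family, one further blank item is enough.

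**Step 4. Tick by item content rather than by whole domain.** Only the first three Sports and leisure items concern sport. The fourth is about travel and the fifth about planning ahead. A man for whom sport and work or study do not apply, and who ticks only the items that fit, marks 3+4 = 7 and keeps 39, so he has a total. Adding Family planning gives 3+4+4 = 11, leaving 35, and he does not.

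**The case against.** Four points can be made for the plan.

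- **The trigger is demanding.** A reader might infer that simply using the not-applicable boxes costs a subject his total, or that men who neither work, study nor play sport are routinely removed. Steps 3 and 4 do not support that. No single domain is enough, and ticking by item content gives a failure only when all three topics are inapplicable. Whole-domain ticking remains possible, because the instruction names whole domains.
- **The scoring manual is not in the documents.** SAP 7.5.1 and Appendix C defer to the questionnaire's authors, and nothing states that a HAEM-A-QoL not-applicable answer is missing. It is the natural reading, since Appendix C gives it no code, but it is an assumption. What stands is the omission: Appendix E does give an item-by-item rule for not-applicable answers in CHO-KLAT. The condition in 5.1.4 about provision for missing domains does not settle it either, because the only provision printed for the total is the item count.
- **The totals may be right.** A reader might infer that 38 and 63 are errors that should be 35 and 58, because Appendix F says for Hemo-Sat: "Applying a minimum data rule of 75%, at least 27 questions must be answered in order to obtain a total score". That is a different instrument, and Appendix C states no 75% rule for totals. The two figures are unexplained, not shown to be wrong. A flat 35 would in any case still fail the 33-item case.
- **The effect is contained.** These outcomes are neither primary nor secondary, and the protocol tests no hypothesis. Excluded subjects are flagged, the scores are listed, and SAP 5.1.3 shows the baseline mean for the same subjects as each visit summary.

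These points limit the reach of the problem. None of them gives a reason to discard a domain score that meets its own minimum.

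**Conclusion.** The concern holds for the exclusion rule. On the printed text alone, 5.1.4 can remove 10 HAEM-A-QoL or 12 HAEMO-QoL domain scores that Appendix C would accept, because the totals demand 1 and 2 more items than the domain minima sum to. On the further assumption that not applicable is unscored, a HAEM-A-QoL respondent who skips nothing can lose 7 or 8 complete domains, but only with at least 9 of the 13 boxes marked. The scored HAEMO-QoL domains have no such boxes, so this second route does not apply to them.

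It would be tempting to conclude that the quality-of-life summaries are biased towards more active subjects. The documents give no frequency of not-applicable answers, so neither the number affected nor the direction of bias can be established. The loss is plausibly non-random, and no more can be said. The consequence is confined to descriptive patient-reported summaries. It is worth correcting because the correction is easy.

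**What to change.** 1. In SAP 5.1.4, delete the exclusion from domain summaries for HAEM-A-QoL and HAEMO-QoL, and summarise each domain whenever its own Appendix C minimum is met. The sentence also covers Hemo-Sat, so reword it to say what still applies there.
2. In Appendix C, state how a HAEM-A-QoL not-applicable answer is scored and whether it lowers the required item count.
3. Confirm 38 of 46 and 63 of 77 against the instruments' scoring manual and cite the source. Do not replace them with a 75% figure without that check.

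The cost is SAP wording and one derivation flag. The number of subjects will differ between domains and between domains and total. SAP 5.2.1 already calls for the count of non-missing values in each summary, so this will be visible.

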5.2. Data Summaries

5.2.1. Continuous Variables

Continuous variables will be summarized using descriptive statistics including the number (n) of non-missing values, mean, standard deviation (SD), median, minimum, and maximum. Where specified in the table shells, the 25th and 75th percentiles will also be provided. Means, medians, and the 25th and 75th percentiles will be presented to one decimal place beyond that with which the data was captured. SDs will be presented to 2 decimal places beyond that with which the data was captured. Minimum and maximum will be displayed to the same number of decimal places as that with which the data was captured.

Unless impractical within a given table, statistics will be aligned by the decimal place in the summary tables (even though not necessarily displayed in this manner in the table shells).

5.2.2. Categorical Variables

Categorical variables will be summarized by counts and percentages. All percentages will be rounded to 1 decimal place. The percentage will be suppressed when the count is 0. Unless specified otherwise, the denominator for all percentages will be the number of subjects (or other experimental unit, e.g. bleeding episodes) in each treatment regimen or overall with non-missing data for a given summarization. This n will be included with categorical summaries unless the same variable is also being summarized with descriptive statistics, in which case 'n' will already be provided.

5.3. Study Periods

5.3.1. Treatment Regimens for Analysis

For the purpose of analysis, the treatment regimen in study 9HB01EXT means the actual treatment regimen(s) that subjects follow over the course of the study (i.e., not necessarily the regimen they started on). For example, a subject who starts the study on the individualized prophylaxis regimen and switches to the weekly prophylaxis regimen will appear in both the individualized prophylaxis and weekly prophylaxis regimens in the summaries based on the time he spent in the respective regimens.

Start and End of Treatment Regimens

At the start of study 9HB01EXT, the start date and time of the starting treatment regimen is 9HB01EXT Study Day 1 with starting time defined below:

For 9HB01EXT subjects with no gap or a gap of less than or equal to 14 or 7 days:

Starting time is defined as either 1) 1 minute after the last rFIXFc dose on 9HB01EXT Study Day 1 for subjects on a prophylactic regimen in study 998HB102 or 9HB02PED, or 2) 1 minute after the last non-safety follow-up study visit for subjects on the episodic regimen in study 998HB102 or subjects who ended the study in a surgical/rehabilitation period in study 998HB102 or 9HB02PED.

For 9HB01EXT subjects with a gap of greater than 14 or 7 days:

Start time is defined as either 1) time of the first rFIXFc dose on 9HB01EXT Study Day 1 for subjects on a prophylactic regimen at the start of study 9HB01EXT, or 2) 00:01 on 9HB01EXT Study Day 1 for subjects starting study 9HB01EXT on the episodic regimen or in a surgical/rehabilitation period.

The above definition of the start date and time of the starting treatment regimen is applicable for all subjects with the following exceptions:

- For subjects who were on the episodic treatment arm in study 998HB102 and started study 9HB01EXT on the episodic regimen, if there was any dose on 9HB01EXT Study Day 1, then the episodic treatment regimen in study 9HB01EXT will start at the time of that dose.
- For subjects who were on the episodic treatment arm in study 998HB102 and switched to a prophylactic regimen at study 9HB01EXT start, and had a gap of less than 14 days, the prophylactic treatment regimen in study 9HB01EXT will start at the

time of the first prophylactic dose in study 9HB01EXT. The interval from 1 minute after the last non-safety follow-up study visit through 1 minute before the first prophylactic dose in study 9HB01EXT will be imputed as the episodic treatment regimen in study 9HB01EXT.

The end of the last treatment regimen (for subjects who have not changed treatment regimens, it will be the same treatment regimen as they started) will be either 1) the date and time of the last rFIXFc dose for subjects whose last treatment regimen was prophylactic or if they were in a surgical/rehabilitation period in study 9HB01EXT, or 2) 23:59 on the day of the last non-safety follow-up study visit for subjects whose last treatment regimen in study 9HB01EXT was episodic.

Treatment Regimen Changes

During study 9HB01EXT, when a treatment regimen changes, the date of the prescribed change will be recorded on the 'Treatment Regimen Assignment Change Details (TRS3)' form in the eCRF. In the following sections, new treatment regimen refers to the one that the subject was changed to, and the previous treatment regimen refers to the one immediately before the new treatment regimen. The start date and time of the new treatment regimen and the end date and time of the previous treatment regimen are defined in the following three scenarios:

- From one prophylactic regimen to a new prophylactic regimen, the new prophylactic regimen starts at the date and time of the first prophylactic dose in the new prophylactic regimen. The previous prophylactic regimen ends 1 minute before that. If the time of the first prophylactic dose in the new prophylactic regimen is not available, the new prophylactic regimen will start at 00:01 on the day of the first prophylactic dose in the new prophylactic regimen, and the previous prophylactic regimen will end at 23:59 on the day prior to that.
- From the episodic regimen to a prophylactic regimen, the prophylactic regimen starts at the date and time of the first prophylactic dose in the prophylactic regimen. The episodic regimen ends 1 minute before that. If the time of the first prophylactic dose in the prophylactic regimen is not available, the prophylactic regimen will start at 00:01 on the day of the first prophylactic dose in the prophylactic regimen, and the episodic regimen will end at 23:59 on the day prior to that.
- From a prophylactic regimen to the episodic regimen, if there is no prophylactic dose on the day of treatment regimen change recorded in the eCRF, the episodic regimen starts at 00:01 on the day of treatment regimen change, and the prophylactic regimen ends at 23:59 on the day prior to the day of treatment regimen change. If there is a prophylactic dose on the day of treatment regimen change, the episodic regimen starts 1 minute after that prophylactic dose, and the prophylactic regimen ends on the date and time of that prophylactic dose.

Duration of a Treatment Regimen

The duration of a given treatment regimen is the time period from the start of the treatment regimen to the end of that treatment regimen in study 9HB01EXT. The duration will stop and start for each treatment regimen change. If a subject is treated in a given treatment regimen more than once in study 9HB01EXT, the total durations in the same treatment regimen will be added

together. For example, during study 9HB01EXT, if a subject is treated with the individualized prophylaxis regimen and then the weekly prophylaxis regimen and then goes back to the individualized prophylaxis regimen, then his total duration in the individualized prophylaxis regimen will be the sum of the two durations in the individualized prophylaxis regimen. Further details will be provided for individual analysis where needed.

The total duration of time allocated to each treatment regimen will be calculated in minutes and converted to days as the number of minutes divided by 1440.

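### Parent-study prophylaxis subjects who start the extension on-demand have their episodic time back-dated to before Visit 1, which slightly dilutes the episodic ABR and annualized consumption (minor)

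*SAP*

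**What the plan says.** SAP 5.1.1 defines the gap as "Date of Visit 1 for study 9HB01EXT – date of the last day of the parent study". For short gaps, "9HB01EXT Study Day 1 is defined as the last day of the parent study, i.e. either 1) the day of the last rFIXFc dose" when the subject was on a prophylactic regimen in the parent study. SAP 5.3.1 then starts the first extension regimen at "1 minute after the last rFIXFc dose on 9HB01EXT Study Day 1 for subjects on a prophylactic regimen in study 998HB102 or 9HB02PED". It applies this to every subject apart from two listed exceptions, both for subjects from the episodic arm of 998HB102. One of those covers the mirror-image move, parent episodic to extension prophylaxis: the time before the first prophylactic dose "will be imputed as the episodic treatment regimen in study 9HB01EXT". There is no exception for parent prophylaxis to extension episodic.

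SAP 5.3.2 gives the efficacy period the same start, end and duration as the regimen, apart from adjustments that do not concern this case. ABR (7.1.1) and annualized consumption (6.5.4) both divide by efficacy-period days.

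Two neighbouring rules in 5.3.1 treat the start of episodic time differently:
- For gaps above 14 or 7 days, it starts at "00:01 on 9HB01EXT Study Day 1 for subjects starting study 9HB01EXT on the episodic regimen", and 5.1.1 makes that day the first study visit.
- For an in-study switch from prophylaxis, the recorded change date governs: "if there is no prophylactic dose on the day of treatment regimen change recorded in the eCRF, the episodic regimen starts at 00:01". If a prophylactic dose was given that day, it starts 1 minute after the dose.

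**The concern.** SAP 5.3.1 opens by saying that analysis regimens reflect what subjects actually follow, with time credited to each regimen accordingly. A subject leaving parent prophylaxis to go on-demand in the extension has not entered the extension until Visit 1. The short-gap rule nevertheless credits the days since his last parent dose to the episodic regimen.

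Those days are not neutral in the rates. Any rFIXFc given for a bleed in the parent study after the supposed last dose would itself become the last dose and move Study Day 1 forward. Up to Visit 1 the interval therefore adds days to the denominator but no rFIXFc-treated bleed to the ABR numerator and no rFIXFc to the consumption numerator. The bias has a known direction, downward, and it touches two secondary endpoints reported by regimen. It also creates a step: a 998HB102 subject with a 14-day gap carries the back-dated interval, while one with a 15-day gap carries none.

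**Working it through.** The documents give no ABR, sample-size or power figure for this point, so there is nothing to reproduce. The check uses the SAP's own formula.

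**Inputs**
- ABR = bleeds / efficacy-period days × 365.25 (SAP 7.1.1). Consumption has the same form (6.5.4).
- g = back-dated days from the last parent dose to Visit 1. It is at most 14 for 998HB102 and 7 for 9HB02PED (5.1.1).
- T = true episodic days from Visit 1, summed over all episodic spells (5.3.1). Any T above 0 is evaluable (5.3.2). Follow-up runs up to 4 years (Protocol 7.1).
- T and g for individual subjects are not given, so they are assumed over a range.

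**Formula.** With B counted bleeds, all from Visit 1 onward, the rate with the interval excluded is B/T × 365.25 and the reported rate is B/(T+g) × 365.25. The ratio is T/(T+g).

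| T (days) | g = 3 | g = 7 | g = 14 |
|---|---|---|---|
| 90 | 90/93 = 0.968 (−3.2%) | 90/97 = 0.928 (−7.2%) | 90/104 = 0.865 (−13.5%) |
| 365.25 | 365.25/368.25 = 0.992 (−0.8%) | 365.25/372.25 = 0.981 (−1.9%) | 365.25/379.25 = 0.963 (−3.7%) |
| 1461 | 1461/1464 = 0.998 (−0.2%) | 1461/1468 = 0.995 (−0.5%) | 1461/1475 = 0.991 (−0.9%) |

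For scale, assume an on-demand ABR of 20. With g = 14 the plan reports 20 × 0.963 = 19.26 over 1 year and 20 × 0.9905 = 19.81 over 4 years.

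**Who can be affected.** The subject must have been on prophylaxis in the parent study, start the extension on-demand, and have a short but non-zero gap. Under-12s cannot be on-demand (Protocol 5.3), so these subjects come almost entirely from 998HB102. A non-zero gap is plausible even with direct rollover. The parent end-of-treatment visit may serve as Visit 1 (Protocol 7.2.1), but the gap runs from the last dose, and Protocol 7.1.2 recommends at least 72 hours of washout before inhibitor testing.

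**Boundary wording.** The episodic-to-prophylaxis exception applies to gaps strictly below 14 days, whereas the general short-gap rule includes exactly 14. At exactly 14 days such a subject falls back on the general rule, and his time before the first prophylactic dose counts as prophylaxis. This is a separate slip that affects the prophylactic rates, not the episodic ones.

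**The case against.** The strongest reply is that the SAP knowingly accepts drug-covered time as episodic. After an in-study switch with a prophylactic dose on the change day, episodic time starts 1 minute after that dose. That stands. A reader might infer that counting time under residual drug cover is itself the error, but 5.3.1 does not support this, and starting the clock at Visit 1 would not remove such cover. What neither that rule nor the long-gap rule does is start episodic time before the recorded change or before the first extension visit.

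Three other limits also stand.
- A reader might infer that the interval is fully covered. SAP 5.1.1 says that "for the majority of the subjects, the FIX activity would be anticipated to be below 1% after 14 days"; it does not say that activity stays above 1% until then. Protocol 5.3.2 encourages a 1% to 3% trough. At the 82.12-hour half-life (Protocol 5.1.3), and assuming simple mono-exponential decline, 3% falls to 1% in log2(3) × 82.12 = 130 hours, about 5.4 days. A weekly subject at that target could be below 1% from somewhere between day 7 and day 12.4.
- A reader might infer that no counted bleed can occur in the interval. ABR includes bleeds treated with non-study FIX (7.1.1), and a bleed may start in the gap and be treated at or after Visit 1. The last dose also need not be a prophylactic one.
- The ceiling is not the typical case. If Visit 1 followed the last dose by the 72 hours that Protocol 7.1 asks for at clinic visits, g would be 3 and the effect under 1% at one year.

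It can also be argued that a subject who takes no further prophylaxis is in effect on-demand from his last dose. That is arguable clinically, but the SAP does not apply it to in-study switches or to longer gaps.

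**Conclusion.** The point holds as a minor inconsistency with a known direction of bias. For parent-prophylaxis subjects who start on-demand after a short gap, 5.3.1 puts up to 14 days before Visit 1 into the episodic denominator, contrary to its own principle and to its two neighbouring rules. The reduction reaches T/(T+g) when no counted bleed starts in the interval, and is smaller otherwise. Even at g = 14 it is below 4% with a year or more of episodic time; it becomes material only for short episodic spells.

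The result rests on assumed T and g. The number of affected subjects is not given and could be zero. A reader might infer that the trial's conclusions are at risk. The documents do not support that: the primary endpoint is inhibitor development, and no hypothesis is tested (Protocol 16).

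**What to change.** Add a third exception to SAP 5.3.1, carrying the in-study switch rule over to study entry. For subjects on prophylaxis in the parent study who start 9HB01EXT on the episodic regimen after a short gap, the episodic regimen and efficacy period start at 00:01 on the day of Visit 1, or 1 minute after a prophylactic dose given that day. Leave the interval from the last parent dose to that start out of the episodic denominator, and do not count bleeds with onset in it in the episodic numerator. Such bleeds can still be shown in the listings.

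Separately, extend the episodic-to-prophylaxis exception to include a gap of exactly 14 days, so that it matches the general rule.

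The cost is a few lines of SAP text and a small program change. Study Day 1 and the safety period (5.3.4) need not move. Episodic ABR and consumption rise slightly for affected subjects. Their duration of dosing in 7.3.2, which runs from the start of the first regimen, shortens by g.
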